4.4. Primary Analyses and Methodology

To address the primary study objective, this section describes the primary analysis determining the rates of COVID-19-related hospitalization or death among bamlanivimab-treated patients.

Primary Efficacy Outcome Analysis: COVID-19-Related Hospitalization or all-cause Death up to Days 29, 60, and 90

The primary analysis will determine the number and proportions of the bamlanivimab-treated patients with a COVID-19-related hospitalization or all-cause death up to Days 29, 60, and 90 (binary outcome).

Ninety-five-percent confidence intervals (CIs) for hospitalization or all-cause death proportion at Days 29, 60, and 90 will be provided. The 95% CIs will be constructed using the asymptotic method without continuity correction (that is, normal approximation to the binomial distribution).

Sensitivity Analyses for the Primary Objective

In addition to the above primary analysis, the following analyses maybe performed as sensitivity analyses.

Time to Event

Time to the first COVID-19-related hospitalization or all-cause death at Days 29, 60, and 90 will be calculated as the duration from the infusion date to the first date of admission to COVID-19-related hospitalization or death date (the duration = the first date of admission to COVID-19-related hospitalization or death date plus - infusion date +1). For patients who do not experience a COVID-19-related hospitalization or death up to Day 29 (60, 90) following the infusion date, a

censoring date is defined as the earliest of 29 (60, 90) days following the infusion date, or the early discontinuation date (such as due to lost to follow-up or drop out). For those who are not admitted due to COVID-19 or have not died up to Day 29 (60, 90), the outcome will be treated as a censored response after Day 29 (60, 90). Cumulative incidence of COVID-19-related hospitalization or all-cause death at Days 29, 60, 90 will be estimated based on Kaplan-Meier estimates. Kaplan-Meier curves will also be plotted. The number of patients who experienced COVID-19-related hospitalization or die from any cause, cumulative incidence of each endpoint, 95% CI of the cumulative incidence, and number of patients at risk over time will be reported at Days 29, 60, and 90.

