3.2. Data Collection

Data for bamlanivimab-treated patients will be captured at the infusion visit (Day 1), at 24 hours post-infusion (Day 2), and at subsequent follow-up periods (Days 29, 60, and 90). Case report form (CRF) data documented within the EDC system will be captured on-site on Day 1 and via telephone call on Days 2, 29, 60, and 90. The EMR records will be extracted during 1 year prior to and 90 days post the infusion date.

Sample Size Determination

Due to early termination, the study enrolled 109, rather than the anticipated 500-3000, bamlanivimab-treated patients. Given that the revised primary objective is to determine the proportion of patients with COVID-19-related hospitalization or all-cause death up to 29 days among bamlanivimab-treated participants and without the use of a comparison group, the observed sample size was 109 participants. This achieved sample size of 109 participants will allow for estimating the proportion with a precision of $\pm 4.4\%$ ($=1.96*\sqrt{(p(1-p)/n)}$) under the assumption of normal approximation of a binomial distribution at a 2-sided significance level of 0.05 and 6% of the true rates of COVID-19-related hospitalization or all-cause death.

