4.3. Populations for Analyses

The analysis population includes all patients who meet inclusion criteria and receive bamlanivimab in a single IV infusion of 700 mg or less.

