4.5. Secondary Analyses

To support the secondary study objectives, analyses will include:

- determination of the proportions of patients with COVID-19-related hospitalizations up to Days 29, 60, and 90
- COVID-19-related ER visits up to Days 29, 60, and 90
- Description of AEs and SAEs up to 2 hours, 24 hours, Days 29, 60, and 90.

Descriptive analyses for these secondary objectives will follow the same statistical methodology as used for the primary analysis.

COVID-19-related ED visits, AEs, and SAEs defined in Section 3.5 will be summarized by numbers and percentage up to 2 hours, 24 hours, and 29, 60, and 90 days after infusion. A listing of AE data for patients at any time during the study will be provided, including age, gender, race, the description of AE, start date, stop date, time from infusion (in days), and severity.

Exposure to Therapy

Exposure to therapy will be listed, including timing of infusion, planned dose, total dose administered, treatment interrupted, and reason for interruption. Exposure to therapy will be represented as the total number of complete and incomplete infusions and will be summarized using descriptive statistics.

Adverse Events

Although all AEs after signing the ICF are recorded by the site in the CRF/EDC, SAE reporting to the sponsor begins after the participant has signed the ICF and has received study intervention. However, if a SAE occurs after signing the ICF, but prior to receiving study intervention, it will be reported within the SAE reporting timeframe if it is considered reasonably possibly related to study procedures.

Adverse events will be coded according to the Medical Dictionary for Regulatory Activities (MedDRA). Summaries of AEs will include the number of participants with at least 1 AE. When reporting by System Organ Class (SOC) and Preferred Term (PT), the reports will present the SOC in alphabetical order; PTs within the SOCs will be presented in order of decreasing frequency of occurrence overall. A patient with multiple AEs (different PTs) coded to the same SOC will be counted only once for that SOC but will be counted each time for different PTs within that SOC. A patient with separate events of the same PT will be counted only once in the frequency tables for that PT.

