4.6. Handling of Missing Data or Dropouts

Due to low study enrollment, all objectives are descriptive in nature. Summary statistics will be based on nonmissing data.

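### The planned 95% interval for the primary proportion (uncorrected normal approximation) covers 89.2% at the SAP's own n=109 and 6%, and nearly all misses fall below the true rate

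*SAP*

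**What the plan says.** SAP section 4.4 makes the primary result the number and proportion of treated patients with the event up to Days 29, 60 and 90, with 95% confidence intervals. On the method it says: "The 95% CIs will be constructed using the asymptotic method without continuity correction". A parenthesis identifies this as the normal approximation to the binomial. No exact or score interval is given as an alternative, and there is no rule for few or zero events.

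The only other interval for this endpoint comes from a Kaplan-Meier analysis. That analysis is optional ("the following analyses maybe performed as sensitivity analyses") and its interval method is not stated.

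Section 4.5 extends the choice: "Descriptive analyses for these secondary objectives will follow the same statistical methodology as used for the primary analysis".

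The Sample Size Determination text under section 3.2 rests on the same approximation. It says "This achieved sample size of 109 participants will allow for estimating the proportion with a precision of" ±4.4%, "under the assumption of normal approximation of a binomial distribution at a 2-sided significance level of 0.05", with an assumed "6% of the true rates of COVID-19-related hospitalization or all-cause death".

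Two further statements affect the denominator. Section 4.3 says "The analysis population includes all patients who meet inclusion criteria and receive bamlanivimab", and section 4.6 says "Summary statistics will be based on nonmissing data". Either could bring the analysed number below 109.

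**The concern.** The Wald interval is symmetric about the observed proportion, and its width is computed from that same proportion. When events are few, a low count produces both a low estimate and a narrow interval, so the upper limit falls short of the truth too often. With about 6 or 7 events expected, that is the situation here.

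The control group and all comparisons have been dropped, so the proportion and its interval are the whole primary result, and this is the only interval the plan commits to. If its true level is well under 95% and the errors go mainly one way, the report will understate how high the hospitalization-or-death rate in treated high-risk patients could plausibly be.

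**Working it through.** **Inputs.** n = 109, p = 6%, two-sided 0.05 (SAP, Sample Size Determination under 3.2). Interval method from SAP 4.4. All other rates and sample sizes below are assumptions, used to show the range.

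**1. The plan's own precision figure.** The SAP formula is 1.96 × √(p(1−p)/n).
- At n = 109: 1.96 × √(0.06 × 0.94 / 109) = 4.46 points. The SAP prints 4.4; rounding gives 4.5.
- At n = 112: 1.96 × √(0.06 × 0.94 / 112) = 4.40 points.

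The gap is small and looks like truncation. The symmetric form matters more: a Wilson interval at an observed 6% runs from 2.9% to 12.1%, that is −3.1/+6.1 points.

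**2. Expected events.** 109 × 0.06 = 6.54.

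**3. Exact coverage at n = 109, p = 6%.** For X ~ Binomial(109, 0.06), sum P(X = x) over every x whose interval contains 6%.
- The Wald interval lies wholly below 6% for 0 to 3 events (at 3 events it is −0.3% to 5.8%). P(X ≤ 3) = 10.19%.
- It lies wholly above 6% for 14 or more events (at 14 events it is 6.6% to 19.1%). P(X ≥ 14) = 0.57%.
- Coverage = 100 − 10.19 − 0.57 = 89.24%.

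Within the low-side misses, 1 to 3 events give a negative lower limit (10.19 − 0.12 = 10.1%), and zero events gives an interval of 0% to 0% (0.12%).

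| Method | Coverage | Interval wholly below 6% | Interval wholly above 6% |
|---|---|---|---|
| Wald | 89.2% | 10.2% | 0.6% |
| Wilson | 96.0% | 0.9% | 3.1% |
| Clopper-Pearson | 97.7% | 0.9% | 1.4% |

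**4. Sensitivity to n, at p = 6%.**

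| n | Wald | Wilson | Clopper-Pearson |
|---|---|---|---|
| 95–120, mean | 91.7% | 95.3% | 97.1% |
| 95–120, range | 87.5–94.5% | 94.0–97.0% | 96.4–97.8% |
| 104 | 94.3% | 94.0% | 96.6% |
| 105 | 94.5% | 96.5% | 96.5% |
| 106 | 87.5% | 96.4% | 97.8% |

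Over n = 95–120 the Wald misses average 7.5% low and 0.7% high. At n = 100–104 Wald (93.7–94.3%) and Wilson (94.0–94.7%) perform about alike.

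**5. Sensitivity to the rate, at n = 109** (equal weight on a grid of 0.01 points).

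| Assumed rates | Wald mean | Wilson mean |
|---|---|---|
| 5–7% | 92.1% | 95.1% |
| 4–8% | 91.6% | 95.3% |
| 2–10% | 91.3% | 95.4% |

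Wald is below 95% at every grid rate from 3% to 9%. Over 2–10% the minimum coverage is 79.5% for Wald, 92.7% for Wilson and 95.1% for Clopper-Pearson.

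**6. What a reader would see.**

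| Events | Wald | Wilson | Clopper-Pearson |
|---|---|---|---|
| 6/109 | 1.2–9.8% | 2.5–11.5% | 2.0–11.6% |
| 7/109 | 1.8–11.0% | 3.1–12.7% | 2.6–12.8% |

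The Wald upper limit is 1.6 to 1.8 points below the other two, and its lower limit 0.8 to 1.3 points below.

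**The case against.** The strongest reply is that little depends on the interval. The study is descriptive, no hypothesis is tested, the proportion is unaffected, and the counts are reported, so any reader can compute another interval. At 6/109 the limits move by less than two points. That is a fair account of the consequence and it limits the weight of the point. It does not justify labelling as 95% an interval that covers about 92% on average, when that interval is the only committed statement of uncertainty for the primary result.

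A second reply is that 89.2% sits just past a drop in the sawtooth. This is true: losing 4 to 9 patients from the denominator would give 93.7–94.5%, and Wilson is itself slightly under 95% at n = 100–104. The average shortfall at 6% is about 3 points, not 6. But Wald stays below 95% at every n from 95 to 120, so the shortfall does not depend on picking n = 109.

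A third reply is that simply adding a continuity correction would do. At n = 109 and 6% it gives 95.7%, but over n = 95–120 it averages 94.2%, and over rates of 2–10% it falls to 86.1%. It is not the better repair.

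Two smaller replies stand. Zero events is very unlikely at 6%, and the negative lower limits arise in outcomes already counted as low-side misses, so neither adds separate harm. And section 4.5 goes on to describe ER visits and adverse events by numbers and percentages only, so the hospitalization proportion is the one secondary result that plausibly inherits the interval.

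**Conclusion.** The concern holds and should be fixed. At the SAP's own inputs the planned interval covers 89.2%. With n varied from 95 to 120 at 6%, it misses about 8% of the time on average, and about ten in eleven of those misses lie below the true rate (7.5% against 0.7%). The harm is confined to the stated uncertainty of a descriptive result.

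The size rests on the 6% planning rate and a denominator near 109. Both could differ in the data, and individual coverage values move with them. Under-coverage itself persists at every n checked from 95 to 120 at 6%, and at every rate checked from 3% to 9% at n = 109.

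**What to change.** - In SAP 4.4, replace the asymptotic interval with one named score or exact interval for the primary proportion at Days 29, 60 and 90. Wilson averages close to 95% but dips to 92.7% at some rates. Clopper-Pearson does not fall below 95% but is wider. Either is defensible if it is the only one named; the choice depends on whether average or guaranteed coverage is wanted.
- In SAP 4.5, state that the same method applies to the hospitalization proportion and to any other secondary proportion reported with an interval.
- In the Sample Size Determination text, restate the precision with the chosen interval as lower and upper limits. If the existing formula is kept, correct its result to 4.46 points.
- If the analysis has already been run, report the chosen interval beside the planned one as a documented change.

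The cost is one sentence in 4.4, a matching statement in 4.5, the precision line and one software option. At 6/109 the width goes from 8.56 points (Wald) to 8.94 (Wilson) or 9.55 (Clopper-Pearson), and the interval becomes asymmetric. No new data are needed and the point estimate does not change.

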3.5. Endpoints

The study endpoints are defined as at 29, 60, and 90 days of the date of the bamlanivimab infusion.

[figure not shown]

Figure 3.2. Illustration of the timeline for study participants.

The following endpoints are defined based on the EDC and EMR data.

- Primary endpoint:
 - COVID-19-related hospitalization (defined as ≥ 24 hours of acute care for COVID-19) or all-cause death up to 29, 60, and 90 days
- Secondary endpoints:
 - COVID-19-related hospitalization, defined as ≥ 24 hours of acute care, up to 29, 60, and 90 days
 - COVID-19-related emergency department (ED) visits up to 29, 60, and 90 days
 - Adverse Events (AEs) or Severe Adverse Events (SAEs) up to 2 hours, 24 hours, and 29, 60, and 90 days

The period of follow-up for ascertainment of these endpoints will be 29, 60, and 90 days following the infusion date. The COVID-19-related hospitalization or all-cause death will be

defined as binary, and secondarily time to event variable will also be included. For time-to-event endpoints, days to the first COVID-19-related hospitalization or death will be calculated from the infusion date. For patients who do not experience a particular endpoint up to 29, 60, and 90 days following the infusion date, a censoring date will be defined as the earliest of

- 29, 60, and 90 days following the infusion date, or
- the early discontinuation date (study participants).

The AEs or SAEs will be collected from the CRF. The proportion of patients with an SAE or AE will be reported.

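### Do the SAP's two ways of counting to Days 29, 60 and 90 put the primary proportion and its Kaplan-Meier check on different windows?

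*SAP*

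**What the plan says.** SAP 3.2 numbers the study days: data "will be captured at the infusion visit (Day 1), at 24 hours post-infusion (Day 2"), then at Days 29, 60 and 90. The protocol's Schedule of Activities uses the same numbering.

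SAP 4.4 makes the primary outcome binary, counted up to Days 29, 60 and 90. Its optional time-to-event sensitivity analysis sets "the duration = the first date of admission to COVID-19-related hospitalization or death date plus - infusion date +1" and reads the Kaplan-Meier curve at Days 29, 60 and 90. For patients who do not "experience a COVID-19-related hospitalization or death up to Day 29 (60, 90) following the infusion date", the "censoring date is defined as the earliest of 29 (60, 90) days following the infusion date" or the early discontinuation date. The next sentence treats event-free patients as censored after Day 29 (60, 90).

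SAP 3.5 counts from the infusion date: "The period of follow-up for ascertainment of these endpoints will be 29, 60, and 90 days following the infusion date".

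SAP 4.5 uses both forms. The bullet reads "COVID-19-related ER visits up to Days 29, 60, and 90", while the text says ER visits, AEs and SAEs "will be summarized by numbers and percentage up to 2 hours, 24 hours, and 29, 60, and 90 days after infusion".

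On data availability, SAP 3.2 states: "The EMR records will be extracted during 1 year prior to and 90 days post the infusion date".

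**The concern.** If infusion is Day 1, Day 29 is 28 days after infusion. A date 29 days after infusion is then Study Day 30, and likewise 61 and 91 at the later landmarks. The SAP uses both counts, once within a single sentence of 4.4, and no readable text says which one fixes the cut-off of the binary endpoint. It also gives no formula for a censored duration.

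The Kaplan-Meier analysis is there to check the primary proportion. A difference between the two should reflect early discontinuation, not a counting rule. If the binary window came from 3.5 and event times from the 4.4 formula, a boundary-day event would be counted in one and missed in the other. Two programmers could also derive windows one day apart.

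**Working it through.** **Inputs.** Infusion = Day 1 (SAP 3.2). Duration = event date − infusion date + 1 (SAP 4.4, ignoring the stray word). Window and censoring at 29, 60 and 90 days from infusion (SAP 3.5 and 4.4). n = 109 and assumed rate 6% (SAP, Sample Size Determination).

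**The plan's own precision figure.** 1.96 × √(0.06 × 0.94 / 109) = 4.46 percentage points. The SAP gives 4.4, which is this value truncated. It serves below as a yardstick.

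**Date arithmetic at the first landmark.**

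| Event date | Duration with +1 | Inside 3.5 window, read literally | Study Day ≤ 29 | Counted by Kaplan-Meier at 29 |
|---|---|---|---|---|
| infusion + 28 | 29 | yes | yes | yes |
| infusion + 29 | 30 | yes | no | no |
| infusion + 30 | 31 | no | no | no |

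Only infusion + 29 is in dispute. The same holds for infusion + 60 (duration 61) and infusion + 90 (duration 91).

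**Illustration (invented data).** 109 patients, no early discontinuation, six early events, one event at infusion + 29, and 102 event-free.

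- Binary window from 3.5, Kaplan-Meier from 4.4: 7/109 = 6.42% against 6/109 = 5.50%.
- Study Day 29 for both: 5.50% and 5.50%.
- 29 days after infusion for both, without the +1: 6.42% and 6.42%.

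The gap in the mixed case is 1/109 = 0.92 points, and 0.92/4.46 is about one fifth of the half-width.

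**Does the censoring rule matter?** With administrative censoring at time 29 or at time 30, every event-free patient is still at risk at time 29. The estimate at 29 is 5.50% in both cases. If events carried the +1 and censored times did not, the late event would fall at time 30, after the administratively censored patients had left the risk set, and the curve would jump to 100%. That jump lies beyond the landmark.

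**How likely is a boundary event?** Expected events by Day 29: 109 × 0.06 = 6.54. Spread evenly over 29 days (an assumption): 6.54/29 = 0.23 on the boundary day. Chance of at least one: 1 − (1 − 0.06/29)^109 = 20.2%. At an assumed 3% rate the figures are 109 × 0.03/29 = 0.11 and 10.7%. A 12% rate is not a fair upper case here: protocol 9.2 assigns it to untreated controls, puts treated patients at no more than 6%, and this SAP analyses only treated patients. The documents give no rate for Days 60 or 90.

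**Internal reading of 4.4.** The binary outcome, the event formula, the landmarks and the sentence on censoring after Day 29 all fit one scale, with infusion as Day 1. On that scale the proportion and the Kaplan-Meier estimate use the same window.

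**The case for a change.** The best case for a change is that the cut-off date of the primary endpoint should not be left to whoever programs it. The fit within 4.4 does not rescue 3.5: on the Day 1 scale the 3.5 window is one day too long, so some text is wrong on any reading. The Version 3 revision history shows the sponsor had already reworded this area to avoid confusion and did not finish. Aligning it would cost a few words and no data, since the EMR extract runs to 90 days after infusion and covers either count.

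What stands is that the wording is mixed and that one sentence could tidy it. Three things weaken the case for requiring it. Figure 3.2, the participant timeline in 3.5 whose follow-up days Version 3 updated, could not be read in the copy reviewed, so it may already show the intended count. The mixed derivation needs an analyst to take one window for the proportion and another for its own sensitivity check, and a curve that jumped to 100% would give away inconsistent event and censoring times. In 4.5 the elapsed-day phrasing sits beside 2 hours and 24 hours and feeds descriptive counts with no planned Kaplan-Meier counterpart, so the mismatch cannot arise there.

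Nor are the two counts equally natural. Dropping the +1 would leave Day 29 meaning infusion + 29 for endpoints and infusion + 28 for visits. It would also give time zero to a hospitalization later on the infusion day, which the protocol's Schedule of Activities collects. The Study Day scale is the one an analyst would reach for.

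**Conclusion.** The inconsistency is real but minor, and no change to the plan is needed. It is a gap in the date convention that analysts fill sensibly, plus a clerical slip: the stray word in the formula does not obscure its meaning.

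The proportion and the Kaplan-Meier estimate differ only under the mixed derivation, and only for an event exactly 29, 60 or 90 days after infusion, at 0.92 percentage points per event with n = 109. Most likely no event is affected at Day 29: 0.23 expected and about a 20% chance of any, given the 6% rate and an even spread, and less if hospitalizations cluster soon after infusion. No figure can be given for Days 60 and 90.

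Either count, used throughout, gives a sound descriptive estimate. There is no control group and no hypothesis test, the Kaplan-Meier analysis is optional, and no decision turns on one calendar day. Writing down a single convention would most likely leave every reported result as it is.

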### 7.2. Participant Discontinuation/Withdrawal from the Study

A participant may withdraw from the study

- at any time at his or her own request
- at the request of his or her designee (e.g., parents or legal guardian)
- at the discretion of the investigator for safety, behavioral, compliance, or administrative reasons, and
- if enrollment in any other clinical study involving an investigational product or enrollment in any other type of medical research judged not to be scientifically or medically compatible with this study.

Discontinuation is expected to be uncommon.

At the time of discontinuation, if possible, an early discontinuation phone call should be conducted to ascertain SAEs/AEs, as described in the SoA (Section [1.3](#)).

If the participant withdraws consent for disclosure of future information, the sponsor may retain and continue to use any data collected before such a withdrawal of consent. If a participant withdraws from the study, they may request destruction of any samples taken and not tested, and the investigator must document this in the site study records.

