### **7.3. Lost to Follow-Up**

A participant will be considered lost to follow-up if he or she repeatedly is unavailable for scheduled visits and is unable to be contacted by the study site. Site personnel or designee are expected to make diligent attempts to contact participants who are unavailable for a scheduled visit or were otherwise unable to be followed up by the site.

Site personnel, or an independent third party, will attempt to collect the vital status of the participant within legal and ethical boundaries for all participants that received study intervention. Public sources may be searched for vital status information. If vital status is determined to be deceased, this will be documented and the participant will not be considered lost to follow-up. Sponsor personnel will not be involved in any attempts to collect vital status information.

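### The optional Kaplan-Meier analysis drops event-free EMR follow-up after early discontinuation but keeps later EMR events, which biases cumulative incidence slightly upward

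*SAP*

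**What the plan says.** SAP 4.4 (Time to Event) opens its censoring rule with a condition: "For patients who do not experience a COVID-19-related hospitalization or death up to Day 29 (60, 90) following the infusion date". For those patients the censoring date is the earlier of the horizon or "the early discontinuation date (such as due to lost to follow-up or drop out". SAP 3.5 has the same structure. Its condition is "For patients who do not experience a particular endpoint up to 29, 60, and 90 days following the infusion date", and the alternative to the horizon is "the early discontinuation date (study participants".

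A further sentence in SAP 4.4 says that patients neither admitted for COVID-19 nor dead by Day 29 (60, 90) are treated as censored after that day. It makes no exception for discontinuers.

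The analysis is optional: "the following analyses maybe performed as sensitivity analyses". The primary analysis is a binary proportion with a normal-approximation 95% CI and has no censoring rule.

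On data sources, SAP 3.5 defines the endpoints from EDC and EMR data, and SAP 3.2 states: "The EMR records will be extracted during 1 year prior to and 90 days post the infusion date". No stop at discontinuation is mentioned.

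The protocol separates two situations that the SAP rule merges. On withdrawal, Protocol 7.2 says: "If the participant withdraws consent for disclosure of future information, the sponsor may retain and continue to use any data collected before" that withdrawal. On loss of contact, Protocol 7.3 defines lost to follow-up by missed visits and failed contact, and adds: "If vital status is determined to be deceased, this will be documented and the participant will not be considered lost to follow-up".

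**The concern.** Early discontinuation ends study contact. It does not by itself end the EMR record, which SAP 3.2 extracts to Day 90. A participant who cannot be reached, but whose record runs to Day 90 with no admission, has been observed event-free to Day 90. The SAP nevertheless censors that participant at discontinuation. A second participant who is unreachable from the same day, and whose record shows an admission a week later, counts as an event on the admission date. The two have equal follow-up and differ only in outcome, yet one leaves the risk set early and the other does not. Protocol 7.3 works the same way for deaths: a participant found dead is no longer lost, while an unreachable survivor is.

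Kaplan-Meier estimation requires that time at risk not be decided by what happens later. Here it is, and the error has a known direction: the numerator is complete and the risk set is too small.

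The extra sentence in SAP 4.4 adds ambiguity. Under it, an event-free discontinuer is censored after the horizon. Under the sentence before it, the same patient is censored at discontinuation. Two programmers could produce different curves from the same data.

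**Working it through.** **Yardstick from the plan.** SAP 3.2 (Sample Size Determination) states a precision of ±4.4% for n = 109 and p = 6%. Recomputed: 1.96 × √(0.06 × 0.94 / 109) = 4.46%. The stated figure agrees by truncation.

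**Inputs.** n = 109 is from the SAP. The documents give no number of discontinuers and no number of later events, so these are assumed: 5 events in patients who do not discontinue, k discontinuers, and j of the k with an EMR event after discontinuation but before Day 29. Two cases are used: k = 5, j = 2 and k = 10, j = 3. For scale, Protocol 9.2 allowed for 5% loss, and 5/109 = 4.6%.

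**Three handling rules for Day 29 cumulative incidence.**

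1. *EMR follow-up for all.* Nobody is censored before Day 29, so the estimate is (5 + j)/109.
2. *SAP as worded.* The j later events count. The k − j event-free discontinuers leave the risk set at discontinuation.
3. *Censor first.* All k discontinuers are censored at discontinuation and the j later events are lost. The SAP does not say this. It is shown because a programmer could do it.

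The result depends on when discontinuation occurs, so two timings are used. *Late* means after the 5 other events and before the j later ones. *Early* means before any event.

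**Rule 2, late.** 1 − (104/109) × [1 − j/(104 − (k − j))]
- k = 5, j = 2: 1 − (104/109) × (99/101) = 6.48%
- k = 10, j = 3: 1 − (104/109) × (94/97) = 7.54%

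**Rule 2, early.** (5 + j)/(109 − (k − j))
- k = 5, j = 2: 7/106 = 6.60%
- k = 10, j = 3: 8/102 = 7.84%

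**Rule 3.** Late: 5/109 = 4.59%. Early: 5/(109 − k), which is 5/104 = 4.81% or 5/99 = 5.05%.

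| Case | Rule 1: EMR for all | Rule 2: SAP as worded | Rule 2 minus Rule 1 | Rule 3: censor first |
|---|---|---|---|---|
| k = 5, j = 2 | 7/109 = 6.42% | 6.48 to 6.60% | +0.05 to +0.18 points | 4.59 to 4.81% |
| k = 10, j = 3 | 8/109 = 7.34% | 7.54 to 7.84% | +0.20 to +0.50 points | 4.59 to 5.05% |

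**A more extreme case.** With 6 other events, 11 discontinuers at Day 2 and 1 later event, Rule 2 gives 7/(109 − 10) = 7.07% against 7/109 = 6.42%, a difference of 0.65 points.

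**A null case.** If no discontinuer has a later event and all discontinue after the last event, the three rules agree.

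**The case against.** The strongest case against is that the plan already protects what matters. The censoring date applies only to patients without the endpoint, so no known event is lost. The analysis is optional and descriptive. Protocol 7.2 expects discontinuation to be uncommon. The shift is small beside a half-width of about 4.4 points. SAP 3.2 also gives an extraction window without saying that extraction continues after discontinuation, and Protocol 7.2 addresses only data collected before consent for disclosure is withdrawn. All of this stands. It limits the point to a small defect, but it does not justify making time at risk depend on outcome, or resolve the two conflicting sentences in SAP 4.4.

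A reader might infer more than the documents support, in three ways:

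- *That known admissions and deaths are discarded.* The opening condition in both sections contradicts this. It would be true only under Rule 3, a misreading that the SAP should rule out.
- *That the primary rate is biased downward.* The primary analysis is a binary proportion with no censoring rule, and the bias in the Kaplan-Meier estimate as worded is upward.
- *That censoring is informative because sick patients become unreachable.* The documents give no counts of, or reasons for, discontinuation that would show this. Protocol 8.2.2 keeps an admitted participant in the study, and Protocol 4.1 continues assessments after admission.

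**Conclusion.** The point holds as a modest correction to an optional sensitivity analysis. As worded, SAP 3.5 and 4.4 keep EMR events after discontinuation and discard event-free EMR time after discontinuation, so Kaplan-Meier cumulative incidence is biased slightly upward. The size is roughly 0.1 to 0.5 percentage points for 5 to 10 discontinuers among 109, and more only if discontinuation is both frequent and very early. This rests on assumed counts and on the EMR being available for discontinuers who have not withdrawn consent for disclosure.

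The ambiguity could matter more than the bias. In the two cases above, a censor-first program would give an estimate about 1.6 to 2.8 points below full EMR follow-up (6.42 − 4.81 = 1.61; 7.34 − 4.59 = 2.75). That is a risk of loose wording, not something the plan prescribes.

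**What to change.** In SAP 3.5 and 4.4:

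- Set the censoring date to the earliest of Day 29 (60, 90), the end of EMR coverage, or withdrawal of consent for disclosure of future information. Loss of phone contact alone should not end follow-up.
- Count EMR events and event-free EMR time alike up to that date, with the same end date for deaths and survivors.
- Reconcile the sentence that censors event-free patients after the horizon with the new rule, so that only one instruction remains.
- State that participants with EMR coverage stay in the denominator. SAP 4.6 bases summaries on nonmissing data but does not say whether an unreachable participant with an EMR record is missing.

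The cost is a few lines of SAP text and one derived date, with no new data. The limitation to state in the report is that admissions outside the health system are unseen once phone contact ends, so event-free EMR time after that point is somewhat less certain than time confirmed by a call.
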